### **9.9.1 Adverse Events**

Adverse events will be recorded on the case report forms by the Investigator using verbatim terms that best describe the event. A TEAE is an adverse event with an onset on or after initiation of

trial product, or an adverse event present at initiation of trial product that worsens (*i.e.*, increase in severity: On-Study Grade > Baseline Grade; or relationship to trial product is reported as a possible, probable, or definite). Verbatim descriptions of TEAEs will be mapped to Medical Dictionary for Regulatory Affairs (MedDRA) Version 20 or newer and graded according to NCI-CTCAE, Version 5. All TEAEs (to include SAEs and AESIs) occurring from the first dose through 30 days of last dose of trial product, if unrelated to trial product or non-serious, and all trial product related SAEs and AESIs through 100 days of last dose of trial product, will be summarized by system organ class, and preferred term and further by NCI-CTCAE grade. On subject-based AE tables, for each specific TEAE, a subject will be counted only once under the maximum severity experienced. Similar summaries will be provided for all Grade 3 or higher TEAEs, SAEs, and AEs that lead to discontinuation of trial product. All AEs will be included in the subject listings. Separate listings of subjects that discontinue trial product due to an AE, and listings of subjects with SAEs and deaths will also be presented.

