A TEAE is an AE with an onset on or after initiation of trial product, or an AE present at initiation of trial product that worsens. This includes all AEs occurring from first dose of trial product through 30 days after of last dose of trial product, if unrelated to trial product or non-serious. All trial product-related SAEs and AESIs through 100 days after the last dose of trial product will be counted as TEAEs.

Related TEAEs

A TEAE is determined to be related to trial product for the purpose of CSR reporting if assessed by the investigator as possible, probable, or definitely related to trial product. If a relationship is missing and the TEAE started after the initiation of an individual trial product, then the TEAE will be analyzed as being related to that individual trial product. Relationship will be collected separately for MVA-BN-CV301, FPV-CV301, and atezolizumab.

Serious Adverse Events

AEs that meet the seriousness criteria as described in Section 8.1.4 of the trial protocol are considered serious adverse events (SAEs). Collection of SAEs begins at the signing of the ICF and continues for 30 days after the last treatment with trial product for unrelated events, and for 100 days after the last dose for treatment-related events.

Severe Adverse Events

AEs are graded for severity using the National Cancer Institute's Common Terminology Criteria for Adverse Events (NCI CTCAE) version 5.0. Levels include 1: Mild, 2: Moderate, 3: Severe, 4: Life Threatening, and 5: Death. For analysis, severe AEs will include AEs \geq Grade 3.

Adverse Events of Special Interest

AEs of special interest (AESIs) include Immune-mediated AEs (IMAEs) and cardiac events but may also include other events based on the opinion of the investigator. Autoimmune diseases and immune-mediated clinical syndromes, occurring after first treatment with trial

product, will be reported as potential IMAEs. In addition, cardiac events are considered AESIs. A Cardiac AESI is defined as:

- Any cardiac sign or symptom (attributed by the investigator to be cardiac related) developed since the first vaccination
- ECG abnormalities determined to be clinically significant developed since the first vaccination

Additionally, for atezolizumab AESIs will be reported based on the manufacturer's requirements (See trial protocol section 8.1.3 for further details).

1 Introduction

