4.3.4 Assignment of AEs to Treatment Period

Each AE will be assigned to a treatment period using date of vaccination (or infusion if this is the final treatment) and date of onset of AE:

- All AEs beginning before the first treatment with trial product will be classified as pre-treatment AEs belonging to the Screening Phase.
- All AEs starting on the day of first MVA-BN-CV301 vaccination until the day prior to the first FPV-CV301, or until early treatment termination, will be assigned to the MVA Vaccination Period.

- All AEs starting after the first FPV-CV301 vaccination through 30 days post-last trial product, or until early termination, will be assigned the FPV Vaccination Period.
- All AEs starting after the first dose of trial product through 30 days post last trial product (CV301 or atezolizumab, whichever is latest) will be included in the Overall Treatment Period.
- Related SAEs and AESIs starting after 30 days but prior to 100 days after the last trial product dose will be assigned to the FU phase of the trial. Other AEs (i.e., not serious or unrelated) occurring during the same time period will be assigned to the FU phase but excluded from tables, if collected, as they are not considered treatment emergent.

If an AE coincides with the date of a vaccination, the AE will be assigned to the treatment period corresponding to the vaccination on this date to be conservative.

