4.4.8 Safety Variables and Analyses

4.4.8.1 Adverse Events

Variables

- **Baseline Signs and Symptoms (pre-treatment AEs)**
Any AE recorded between ICF signing and first treatment with trial product, regardless of seriousness.
- **TEAEs**
- **SAEs**
- **AESIs**
AESIs include IMAEs and Cardiac events. IMAEs will be collected from the “Potential IMAE” CRF page where the question “Does this event have an immune-mediated etiology or an immune-mediated component?” on the IMAE page is marked as “Yes.” Cardiac AESIs will be identified where “AESI?” is marked as Yes on the AE CRF page. As events coded as “Cardiac disorders” per MedDRA SOC and ECGs with clinically significant abnormalities are considered AESIs, cross checking will be performed to ensure all clinically significant ECG results have a corresponding AE in the database prior to database lock. In addition, Troponin I laboratory testing will also be cross checked versus the AE page in the CRF if results are deemed clinically significant by the investigator.
- **Relationship to trial product (MVA-BN-CV301, FPV-CV301, atezolizumab)**
Relationship is collected as unrelated, unlikely, possibly, probably, or definitely related on the AE CRF page. AEs reported as possibly, probably, or definitely related, along with any missing relationship values, will be summarized as related to the treatment of interest. For overall trial product relationship summaries, if any of the three individual trial products are considered related to the AE, the overall relationship will be defined as related to trial product.
- **Severity of AEs (per CTCAE v5.0 grade)**
TEAEs will be categorized as 1: Mild, 2: Moderate, 3: Severe, 4: Life Threatening, or 5: Death on the AE CRF page. For summaries, severe AE displays will include all AEs \geq Grade 3
- **TEAEs leading to Treatment Discontinuation**
Treatment discontinuation will be identified as an AE with an action taken of “Drug Withdrawn” for any of the three trial products.
- **TEAEs leading to Death**

TEAEs with either an outcome of “Fatal” or a severity of “5: Death” will be considered TEAEs leading to death.

Analyses

Summary tables will be presented by treatment period (MVA Vaccination Period, FPV Vaccination Period, and Overall Treatment Period), cohort, and overall including frequency and incidence of AEs, and ordered by descending incidence of SOCs and PTs for the following categories:

- Any TEAEs
- Non-Serious TEAEs occurring in $\geq 5\%$ of either cohort or overall

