- Related TEAEs, including the following subcategories:
 - TEAEs related to MVA-BN-CV301
 - TEAEs related to FPV-CV301
 - TEAEs related to atezolizumab
 - TEAEs related to trial product
- TEAEs \geq Grade 3
- Related TEAEs \geq Grade 3
- SAEs
- Related SAEs
- AESIs, including IMAEs and Cardiac Events
- Related AESIs
- TEAEs leading to discontinuation of treatment

In addition to the above summary categories, listings will also include the following:

- Baseline Signs and Symptoms
- TEAEs leading to death
- Post-treatment period SAEs and AESIs

A summary table of TEAEs will be created for the following categories: TEAEs, SAEs, AESIs, Related TEAEs, Severe TEAEs, Severe and Related TEAEs, Serious and Related TEAEs, TEAEs leading to discontinuation, and TEAEs leading to death. Event counts and subject incidences will be presented within each category and cohort, as well as overall, for the FAS.

The incidence for the above categories will be calculated as the number of subjects developing the specified AE type, divided by the number of subjects in the cohort. The incidence of AEs will also be calculated within each treatment period.

TEAEs will be summarized by SOC and PT and ordered by descending incidence of SOC, as well as descending incidence of PT within SOC. For TEAEs and related TEAEs, summaries will also be provided by

All AEs will be listed by subject, SOC, and PT. Per protocol, no new AEs should be reported during the LTFU phase, with the exception of related SAEs and related AESIs through 100 days post-last treatment. Any other AEs are reported during the LTFU phase will be listed and flagged as non-treatment emergent, but will not be included in the tables.

For summaries by relationship, CRF relationship categories will be dichotomized as related or unrelated per the above definition. Subjects experiencing more than one TEAE within an SOC or PT will be reported for the highest relationship category for the event of interest.

For summaries by severity, the CTCAE v5.0 grade will be used to summarize severe AEs including AEs \geq Grade 3. Again, if a subject has multiple AEs within an SOC or PT the most severe AE will be counted for the event of interest.

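### As written, the SAP's AE period rules put late related SAEs/AESIs, and possibly worsened baseline AEs, outside every period named for the AE summary tables

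*SAP*

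**What the plan says.** Under Treatment Emergent Adverse Event, the SAP's General Definitions state: "All trial product-related SAEs and AESIs through 100 days after the last dose of trial product will be counted as TEAEs". The same paragraph includes an AE present at first dose that later worsens. Protocol 9.9.1 has both elements and adds a reporting requirement: "all trial product related SAEs and AESIs through 100 days of last dose of trial product, will be summarized by system organ class", and also by preferred term and CTCAE grade.

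SAP 4.3.4 assigns each AE to a period from its onset date and the dosing dates. The Overall Treatment Period closes 30 days after the last product of either kind. Beyond that, "Related SAEs and AESIs starting after 30 days but prior to 100 days after the last trial product dose will be assigned to the FU" (meaning follow-up). At the other end, "All AEs beginning before the first treatment with trial product will be classified as pre-treatment AEs belonging to the Screening Phase".

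SAP 4.4.8.1 then specifies the tables: "Summary tables will be presented by treatment period (MVA Vaccination Period, FPV Vaccination Period, and Overall Treatment Period), cohort, and overall". It names post-treatment SAEs and AESIs only among the extra listings. SAP 4.4.7.6 summarizes events between consent and first dose apart from TEAEs. SAP 4.5 declares no change to the protocol's analyses.

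**The concern.** Protocol 8.3.1 gives the reason for the 100-day window: atezolizumab may have a delayed immune effect. Safety of the combination is a secondary objective. A programmer who follows SAP 4.3.4 to the letter closes the Overall Treatment Period table at 30 days and omits the late related events that the window was set up to catch. The TEAE overview table in SAP 4.4.8.1 is not tied to a period, so it would count those events while the period tables by SOC and preferred term would not. Two careful programmers could also build different tables from the same text.

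**Working it through.** The plan states no figure to reproduce here. The check is to run test onsets through the TEAE definition and the SAP 4.3.4 rules together.

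Inputs:
- Planned dosing from the trial procedure schedule: first MVA-BN-CV301 on Day 1, first FPV-CV301 on Day 43, last scheduled product on Day 694.
- Maximum enrollment from SAP 4.1: 33, 35 and 68. Planned Stage 1 sizes: 14 and 13.

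| Test event | TEAE by definition? | Period under SAP 4.3.4 | In a tabulated period? |
|---|---|---|---|
| New AE, Day 10 | Yes | MVA, Overall | Yes |
| New AE, Day 300 | Yes | FPV, Overall | Yes |
| Related SAE, last dose + 30 (Day 724) | Yes | FPV, Overall | Yes |
| Related SAE, last dose + 31 (Day 725) | Yes | FU only | No |
| Related SAE, last dose + 99 (Day 793) | Yes | FU only | No |
| Related SAE, last dose + 100 (Day 794) | Yes | None | No |
| AE from Day -5, worsens on treatment, original onset date kept | Yes | Screening only | No |
| AE from Day -5, does not worsen | No | Screening only | No, correctly |

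**Length of the gap.** 100 - 30 = 70 post-dose days lie outside all three tabulated periods. Days 31 to 99 (69 days) go to FU. Day 100 goes nowhere, because the period rule stops short of day 100 while the TEAE definition includes it.

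**Weight of one omitted subject.** At full enrollment: 1/33 = 3.0% in Cohort 1, 1/35 = 2.9% in Cohort 2, 1/68 = 1.5% overall. If a cohort stops at its planned Stage 1 size: 1/14 = 7.1% or 1/13 = 7.7%.

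**Reach of the worsening problem.** Protocol 8.1.1 treats conditions present up to consent as medical history, and AE collection starts at consent. The second class is therefore limited to AEs that start between consent and first dose and later worsen.

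**Subjects who stop before FPV.** The MVA period closes at early treatment termination, but the Overall Treatment Period runs 30 days past the last product. AEs in that interval count in the Overall column and in neither vaccine column.

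**The case against.** The best defense is that the SAP's authors meant the late related events to be tabulated. The sentence that follows the FU assignment in SAP 4.3.4 excludes only the other follow-up AEs from tables, on the ground that they are not treatment-emergent. SAP 4.4.8.1 repeats that exception. The same section says without a period limit that TEAEs are summarized by SOC and preferred term, describes period incidence as an addition, and introduces the listing of post-treatment events as an extra output. The table shells are in a separate document.

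This stands as evidence of intent, and it rules out the inference that the events vanish from all output. It does not remove the conflict. The section names three periods for its tables, none of which can hold these events, and no rule says which table will.

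On worsened AEs, the objection has more force. If sites open a new record at worsening, the onset falls after dosing and the event is assigned normally. Protocol 8.2.3 points that way for examination findings. The SAP states no recording rule, and the eCRF completion guidelines are separate.

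Three further inferences are tempting but unsupported:
- **That period rates are computed over the whole cohort.** The text reads "divided by the number of subjects in the cohort. The incidence of AEs will also be calculated within each treatment period". The cohort denominator belongs to the first sentence; the second gives none.
- **That FPV-period AEs are cut off when treatment stops early.** The FPV rule runs through 30 days after last product or until early termination, without saying termination of treatment. The General Definitions separate treatment from trial discontinuation and start the 30 days at the last product for early discontinuers.
- **That the understatement can be put as a rate.** Protocol 2.1 quotes 12% immune-mediated AEs with atezolizumab alone in another trial, but neither document gives the share that starts late.

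**Conclusion.** The point holds as a conflict between stated rules. Read as written, SAP 4.3.4 puts related SAEs/AESIs from days 31 to 100 outside every period named for the AE summary tables. That contradicts Protocol 9.9.1, the SAP's own TEAE definition, and the SAP's implication that only other follow-up AEs stay out of tables. For baseline AEs that worsen, the same conclusion is conditional on worsening being kept under the original onset date.

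The size is 70 of 100 post-dose days, and about 3 percentage points per omitted subject within a fully enrolled cohort. The number of such subjects cannot be computed from the documents. The consequence is possible under-tabulation and tables that do not reconcile with the TEAE overview. The efficacy analyses are unaffected. It should be corrected before database lock.

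**What to change.** In SAP 4.3.4 and 4.4.8.1:

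1. Define the overall SOC/PT/grade tables by TEAE status, or extend the Overall Treatment Period to take in related SAEs/AESIs through day 100.
2. Use one day-100 boundary in both places, so that day 100 is included as in the TEAE definition and Protocol 9.9.1.
3. Assign baseline AEs that worsen to a period by the date of worsening, and state how worsening is recorded.
4. As a secondary clarification, for subjects who stop before FPV, run the MVA period to 30 days after last product.

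The cost is SAP wording and a small amount of programming. No new data are needed for items 1, 2 and 4; item 3 needs the date of worsening to be available in the AE record. Reported AE rates may be slightly higher.

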4.3.5 General Consideration for AEs

MedDRA version 21.0 will be used to code AEs, medical history events, and baseline signs and symptoms.

Duration of an AE is calculated as follows:

end date of AE – start date of AE + 1

- In case of missing start date or missing end date, duration will be missing.
- In case of ongoing end date, the duration will not be calculated.

Time interval between vaccination and onset of AE are calculated as follows:

Relative day of onset of AE is calculated as follows:

onset date of AE – most recent vaccination date + 1

- In case of missing start date, no calculation will be performed.

4.4 Analysis and Presentation Methods

4.4.1 General Presentation Methods

All individual data entered in the eCRF and applicable derived data will be listed in subject-level data listings. Listings will be sorted by subject, visit, and parameter, based on the domain presented. Tables will be sorted by parameter and scheduled visit, as applicable.

All tables will be presented by cohort as follows:

- Cohort 1

- Cohort 2
- Overall (Excluding efficacy displays)

With the exception of titer data, continuous measurements will be summarized using the number of observations (n), mean, standard deviation, minimum, median, and maximum (Max). Categorical data will be summarized using frequencies and percentages, unless otherwise stated. Titer data, as well as any data that are log-normally distributed, will be summarized using geometric means and 95% confidence intervals (CIs).

All statistical summaries and analyses will be performed using SAS[®] version 9.3 or higher (SAS Institute, Cary, NC, USA) for Windows .

In the case of repeated assessments at individual time points, all reported values will be presented in subject-level listings based on the CRF visit. For tabular summaries, an individual analysis value will be chosen or created from the multiple values at the time point and flagged at the analysis dataset level per the visiting window in Section 4.3.1. The value used for analysis in the tables will be flagged in the listings.

4.4.2 Considerations for Multicenter Studies

CV301-BLD-001 will be performed in approximately 12 trial sites with a possible range of 27-68 subjects split into 2 cohorts. As the maximum number of subjects per cohort per site is fewer than 10, no by-center analyses will be performed.

4.4.3 Adjustments for Covariates

Due to the baseline differences in the two cohorts, all efficacy analyses will be performed within cohort. Additionally, small sample size prevents further subgroup analyses from being possible.

4.4.4 Adjustments for Multiple Comparisons

Due to the two-cohort, two-stage design of this Phase 2 trial, the primary endpoint of ORR will be tested multiple times. To account for this, the sample size for each cohort was based on a one-sided nominal alpha of 0.025 and 70% power. As each cohort represents an independent test, the overall trial wide type I error rate would remain at or below 0.05 (one-sided). Based on simulations with the two-stage, two-cohort design, the overall type-1 error rate will be approximately 4.7%, and the power for the trial indicating at least one of the two cohorts will be positive given the alternative hypotheses are true, is approximately 91%.

4.4.5 Efficacy Analyses

4.4.5.1 Primary Endpoint

The primary efficacy endpoint for the trial is the ORR, defined as the proportion of subjects achieving CR or PR, whichever occurs first, based on investigator-assessed RECIST v1.1 evaluations. Due to the Simon's 2-stage design, hypothesis testing will occur at the end of Stage 1 (interim analysis), and if successful, at the end of Stage 2 within each cohort.

The success criteria are based on the point estimate of the FAS within each cohort. For Cohort 1, at least 4 responses are required in the first 14 subjects to move to Stage 2. For the final Cohort 1 analysis, the null hypothesis that ORR is no more than 0.23 will be rejected if 13 or more responses are observed in the 33 subjects of the FAS. For Cohort 2, at least 3 responses are required in the first 13 subjects to move to Stage 2. For the final Cohort 2 analysis, the null hypothesis that the ORR is no more than 0.15 will be rejected if 10 or more responses are observed in the 35 subjects of the FAS.

In case the number of subjects in the analysis set(s) exceeds the planned sample size, the success criteria will be chosen to preserve the design type I error rate of 0.025 (one-sided) using the exact 2-stage binomial calculation (replacing p with p_0 in formula [1], [Section 2.6.4.2](#)). Type I error equals 1 minus the result from formula [1] when $p = p_0$.

For the final trial analysis, the number and percentage of subjects in each RECIST v1.1 response category, as well as those with a best objective response of CR or PR, will be summarized based on the FAS. The two-sided 90% exact binomial confidence interval for the ORR will be calculated using the Clopper-Pearson method.

Sensitivity analyses will be explored at the end of the trial based on a repeated analysis for any potential immune-related responses observed, as well as a repeat of the analysis on the EE set. For immune-related response cases, ORR analyses using iRECIST criteria will also be provided. For iRECIST, complete or partial responses are still able to be achieved after an initial unconfirmed progression, whereas with RECIST v1.1 once any evidence of progression is recorded, no further responses can be evaluated. For subjects who are not evaluated by iRECIST criteria, their tumor response based on RECIST v1.1 response guidelines will be used.

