4.1 Planned Sample Size

A Simon's two-stage Minimax design (Simon, 1989) was used to calculate sample size for Cohort 1. Cohort 1 will have a minimum of 14 subjects and a maximum of 33 subjects, with the maximum occurring if and only if at least 4 subjects have an objective response in the first stage of the trial. The alternative admissible 2-stage design (Jung et al., 2004) was used to calculate sample size for Cohort 2. Cohort 2 will have a minimum of 13 subjects and a maximum of 35 subjects, with the maximum occurring if and only if at least 3 subjects have an objective response in the first stage of the trial. The total minimum sample size for the trial is 27, with a maximum of 68 subjects.

The design for Cohort 1, platinum ineligible subjects, is based on a prior published ORR of 23% for atezolizumab monotherapy (Balar et al., 2017). The null hypothesis that the true ORR is 0.23 will be tested against a one-sided alternative. The null hypothesis will be rejected if 13 or more responses are observed in 33 subjects. This design yields an actual 1-sided type I error rate of 0.0244 and power of 0.7027 when the true ORR is 0.43 for the combination.

The design for Cohort 2, platinum refractory subjects who are anti-PD-L1 naïve, is based on a prior published ORR of 15% for atezolizumab monotherapy (Rosenberg et al., 2016). The null hypothesis that the true ORR is 0.15 will be tested against a one-sided alternative. The null hypothesis will be rejected if 10 or more responses are observed in 35 subjects. This design yields an actual 1-sided type I error rate of 0.0249 and power of 0.7092 when the true ORR is 0.33 for the combination.

Based on simulations with the two-stage, two-cohort design, the overall type-1 error rate will be approximately 4.7%, and the power for the trial, indicating at least one of the two cohorts will be positive given the alternative hypotheses are true, is approximately 91%.

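### The 90% Clopper-Pearson interval for the primary ORR ignores the two-stage design: it agrees with the test at 33 and 35 subjects, but under-covers and can contradict the test above plan

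*SAP*

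**What the plan says.** The test. SAP 4.4.4 states that "the sample size for each cohort was based on a one-sided nominal alpha of 0.025 and 70% power", so that the trial-wide error stays at or below one-sided 0.05. In SAP 4.4.5.1 success is a response count in the FAS:

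- Cohort 1: "For Cohort 1, at least 4 responses are required in the first 14 subjects to move to Stage 2", and "the null hypothesis that ORR is no more than 0.23 will be rejected if 13 or more responses are observed in the 33 subjects".
- Cohort 2: "For Cohort 2, at least 3 responses are required in the first 13 subjects to move to Stage 2", and "the null hypothesis that the ORR is no more than 0.15 will be rejected if 10 or more responses are observed in the 35 subjects".

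The interval. SAP 4.4.5.1 and Protocol 9.7.1 then specify: "The two-sided 90% exact binomial confidence interval for the ORR will be calculated using the Clopper-Pearson method". Neither document explains the 90% level, calls the interval descriptive, or adjusts it for the two stages.

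More subjects than planned. SAP 4.4.5.1 re-derives the success count at one-sided 0.025 with the exact two-stage calculation, but leaves the interval as it is. Protocol 9.3 instead restricts the primary evaluation to the first 33 or 35 FAS subjects accrued.

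**The concern.** The ORR and its interval, read against 23% and 15%, will be the trial's headline result. The test accounts for the futility look and works at 2.5% per cohort. The interval ignores the look and is nominally 5% per tail.

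Two things are at stake. The stated confidence level may not hold under the sampling plan actually used. And a report could show a lower limit above the null for a cohort that failed its test, or the reverse.

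**Working it through.** **Inputs.** Cohort 1: Stage 1 n₁ = 14, continue with ≥4; final N = 33, reject with ≥13; null 0.23, alternative 0.43. Cohort 2: n₁ = 13, continue with ≥3; N = 35, reject with ≥10; null 0.15, alternative 0.33. All are from SAP 4.1 and 4.4.5.1.

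**1. Reproduce the stated design.** With r₁ the largest stopping count,

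P(reject; p) = Σ over x₁ > r₁ of b(x₁; n₁, p) × P(X₂ ≥ r − x₁; N − n₁, p).

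- Cohort 1: error 0.0244, power 0.7027. The SAP states "actual 1-sided type I error rate of 0.0244 and power of 0.7027 when the true ORR is 0.43".
- Cohort 2: error 0.0249, power 0.7092, as the SAP states.

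Both reproduce.

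**2. Interval against test at the planned size.** The Clopper-Pearson lower limit is the 0.05 quantile of Beta(x, N − x + 1).

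| Result | Test | 90% CP lower | 95% CP lower | Two-stage 95% lower |
|---|---|---|---|---|
| 12/33 | fails | 22.5% | 20.4% | 20.7% |
| 13/33 | rejects 23% | 25.1% | 22.9% | 23.08% |
| 9/35 | fails | 14.1% | 12.5% | 13.0% |
| 10/35 | rejects 15% | 16.4% | 14.6% | 15.01% |

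The highest stopping results, 3/14 and 2/13, have 90% lower limits of 6.1% and 2.8%, so no early stop puts the interval above the null. The 90% interval therefore clears the null exactly when the test rejects. Its actual one-sided error at the null is the test's own 0.0244 and 0.0249.

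**3. Coverage under two-stage sampling.** Sum the probabilities of all outcomes (stopped with x₁/n₁, or continued with x/N) whose 90% interval misses the true rate.

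- Cohort 1, true ORR 0.466, just above the upper limit of 3/14 (46.57%). Upper limit too low: 0.0497 (any early stop) + 0.0270 (continued, ≤10/33) = 0.0767. Lower limit too high: 0.0368. Coverage = 1 − 0.0767 − 0.0368 = 0.886.
- Cohort 2, true ORR 0.412, just above the upper limit of 2/13 (41.01%). Upper limit too low: 0.0486 (any early stop) + 0.0289 (continued, ≤9/35) = 0.0775. Lower limit too high: 0.0416. Coverage = 1 − 0.0775 − 0.0416 = 0.881. On a finer grid the minimum is 0.880.

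Over true rates from 2% to 90%, the lower-limit error stays below 5% in both cohorts. The upper-limit error is what exceeds its 5%.

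**4. Above the planned size, SAP rule.** Planned Stage 1 is kept, and the success count is the smallest with two-stage error ≤ 0.025.

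| Cohort, N | Test needs | 90% CP clears null from | Error at the CP count |
|---|---|---|---|
| 1, 34 | 14 | 13 (lower limit 24.3%) | 0.0309 |
| 1, 35 | 14 | 13 (23.6%) | 0.0384 |
| 1, 36 | 14 | 14 | 0.0222 |
| 1, 39 | 15 | 14 (23.2%) | 0.0419 |
| 2, 36 | 11 | 10 (15.9%) | 0.0294 |
| 2, 38 | 11 | 10 (15.03%) | 0.0395 |
| 2, 39 | 11 | 11 | 0.0209 |

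The gap is one response where it occurs. It is absent at some sizes (36 and 43 in Cohort 1; 39, 40, 44 and 45 in Cohort 2).

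**5. Two-stage 95% interval.** Rank every futility stop below every continued result, and rank continued results by total. The lower limit solves P(pass Stage 1 and total ≥ x; p) = 0.025. The upper limit solves P(stop, or total ≤ x; p) = 0.025. Results: 13/33 gives 23.08% to 58.36%; 10/35 gives 15.01% to 48.52%. The lower-limit equation uses the same tail probability as the test, so the two agree at any N when both use the same Stage 1 rule.

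**The case against.** The strongest reply is that the interval decides nothing. Success is a response count, the test's error is controlled, and at 33 and 35 subjects the interval never disagrees with it. The coverage loss is in the upper limit, so the limit compared with 23% and 15% is not too favourable for its stated level. The 90% level is also used for PFS milestones, OS and duration of response, so it looks like a house choice. All of this stands. It makes the point one of estimation and reporting, not of the primary test.

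The over-enrolment conflict is also conditional. Protocol 9.3 would cut the analysis at 33 or 35, SAP 2.6.4.1 enrols to those FAS totals, and SAP 4.5 claims no departure from the protocol. But SAP 4.4.5.1 has an explicit rule for larger sets, SAP 2.1 allows replacement of non-evaluable subjects, and Protocol 9.12 allows enrolment until the EE Set is full. While the two rules differ, the conflict cannot be excluded.

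A reader might also infer that the raw ORR is misstated and should give way to the unbiased two-stage estimate (UMVUE). Averaged over early stops, the raw rate is biased by −2.6 points at 23% and −1.2 at 43% (Cohort 1), and −2.3 at 15% and −1.8 at 33% (Cohort 2). Given that a cohort reaches Stage 2, however, the bias is upward: +4.7 and +0.9, and +4.5 and +1.3. At the success lines the UMVUE is higher still: 40.9% against 39.4%, and 31.8% against 28.6%. Replacing the raw rate is a debatable choice, not the correction of an error.

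**Conclusion.** The point holds as one about the interval's nominal level, coverage and behaviour above plan. Described as exact, the 90% interval covers about 88.6% (Cohort 1) and about 88% (Cohort 2) at worst. Under the SAP's over-enrolment rule it can sit above the null for a cohort that misses its cut-off by one response.

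It is tempting to go further and say that the interval doubles each cohort's error and so does not match the test. Two cohorts at 0.05 would give 1 − 0.95² = 9.75%. The documents do not support that reading at the planned size: the interval's error at the nulls is 0.0244 and 0.0249, or 1 − (1 − 0.0244)(1 − 0.0249) = 4.9% across the trial.

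Assumptions: Stage 1 at its planned 14 and 13 subjects, independent binomial responses, and, for the above-plan figures, the SAP rule rather than Protocol 9.3. If Stage 1 is extended, the limits must be recomputed with the realised rule.

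**What to change.** In SAP 4.4.5.1 and Protocol 9.7.1, specify for each cohort a two-sided 95% interval from the two-stage distribution with stage-wise ordering, computed with the same Stage 1 rule and final N as the test. Do not simply raise Clopper-Pearson to 95%: its lower limits of 22.9% and 14.6% include the null at results that the test rejects.

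Keep the raw n/N as the reported ORR. The UMVUE may be added as supplementary, with a note that it exceeds the raw rate at the success lines. Reconcile SAP 4.4.5.1 with Protocol 9.3 on which subjects count when a cohort exceeds 33 or 35. If the 90% interval is kept, state why, and label it descriptive and unadjusted for the two stages.

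The cost is SAP and protocol wording and a few lines of code; conduct, sample size and success rule are unchanged. The price is a less favourable lower limit at the success lines (25.1 − 23.1 = 2.0 points; 16.4 − 15.0 = 1.4 points) and a wider interval: at 13/33, 35.3 points (58.4 − 23.1) against 30.1 (55.2 − 25.1); at 10/35, 33.5 (48.5 − 15.0) against 27.2 (43.6 − 16.4).
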